### 6.4.2 Sample Size Considerations

For all aims, we base our sample size on the unadjusted comparison of paired means, which is a conservative approach. Therefore, given that our statistical analyses will be based on adjusted models and models that specifically take into account within-person correlation in outcomes of interest, we should be sufficiently powered to answer our research questions.

Aim 1: The goal time in range in adolescents with T1D 60% +/- 10% of their time in the target range of 70-180 mg/dL but based on our preliminary work in this population we expect that the mean percent of time in range is around 50-55%. With 16 eligible subjects, we will have 80% power at the two-sided alpha of 0.05 to detect a minimum increase in the expected mean by 7.5% (from 50-55% on standard carbohydrate diet to 57.5-62.5% on low carbohydrate diet - an increase of 1.5 hours per day - an effect size of  $7.5\% \div 10\% = 0.75$ ), using a paired-sample t-test. If we assume 20% attrition, we will need 20 individuals for the study.

Aim 2: Using data from a previously published study, where changes in glucagon levels during 2-step euglycemic-hypoglycemic clamp in youth with T1D were assessed over a period of 1 year(15), we anticipate that with 16 subjects (n=20 with 20% attrition, see aim 1) we will have 80% power at the two-sided alpha of 0.05 to detect a between-diet change in mean glucagon levels of at least 9.5 pg/mL (standard deviation=12.5 pg/mL, effect size of  $9.5 \text{ pg/mL} / 12.5 \text{ pg/mL} = 0.75$ ), using a paired t-test. We will also report the incremental rise and area under the curve (AUC) as well as mean and peak glucagon levels.

Aim 3: Using estimates of variability (standard deviations [sd]=5 during euglycemia and sd=10 during hypoglycemia) from a previous study, with 16 subjects (20 subjects with 20% attrition) we will have 80% power at the two-sided alpha of 0.05 to detect an effect size in the range of 0.75-1.0, using a paired t-test, meaning that when on low carbohydrate diet, subject

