## 6.5 Planned Analyses

### 6.5.1 Primary Objective Analysis

- **Statistical Analyses Aim 1:** The unadjusted between-diet-group comparison of the primary endpoint, percent time in the target range of 70-180 mg/dL during the 2nd week of each diet, will be performed using a two-sided paired t-test. The adjusted analysis will be performed using linear mixed effects (LME) modeling, with a random intercept for each subject, diet effect, and adjusting for a participant's age, BMI and duration of diabetes. The mean adjusted between diet-group difference in percent time in the target range will be reported, along with the surrounding 95% confidence intervals based on 500 bootstrapped samples (2.5th percentile and 97.5th percentile of the distribution). Secondary outcomes, including time spent with hypoglycemia (<54 mg/dL, <70 mg/dL) and hyperglycemia (>180 mg/dL, >250 mg/dL), average sensor glucose level, will be analyzed similarly to the primary outcome. The proportion of days with elevated fasting  $\beta$ -hydroxybutyrate levels ( $\geq 0.6$  mmol/L) during each diet period will be compared using paired-proportions z-test in the unadjusted analysis and using generalized linear mixed effects (GLMM) modeling (a random intercept, link=logit for the binary outcome yes/no elevated levels with Bernoulli distribution) with covariates of age, BMI, and duration of diabetes. GLMM will also be utilized in the comparison of the number of episodes of diabetic ketoacidosis and severe hypoglycemic events during each period (a random intercept, link=log for a count outcome with Poisson distribution). Statistical analyses for all aims will be implemented using R and SAS 9.4 (Cary, NC) statistical software. Statistical significance will be established at the two-sided alpha of 0.05.

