### 6.5.2 Secondary Objectives Analyses

- **Statistical Analysis Aim 2:** Appropriate mathematical transformations (e.g., natural log or square root) will be applied to each outcome of interest, as necessary, to normalize the distribution. A paired t-test will be used in the unadjusted comparison of the primary outcome, mean levels of glucagon, during each diet period. LME will be used to model the trajectories of change in mean levels of glucagon over time (baseline, 15, 30, 45, 60 minutes) during each diet period and compared between diets. We will use the Likelihood Ratio Test (LRT, a mixture of two chi-square distributions with restricted maximum likelihood – RML - estimation) to select between an LME model with just a random intercept or an LME with a random intercept and slope. The mean response will be modeled using parametric (linear and polynomial effects of time) and semi-parametric (piece-wise linear or quadratic splines) effects of time, adjusting for participants' age, BMI, and duration of diabetes. The best model will be chosen based on its fit to the data (LRT for nested models and Akaike Information Criterion, AIC, for not-nested models).

Effect sizes will be reported as the between-diet differences with bootstrapped 95% CIs. Secondary outcomes of interest will also be modeled similarly.

- **Statistical Analysis Aim 3:** Using the validated Edinburgh Hypoglycemia Symptom questionnaire, participants will be asked to verbally rate their hypoglycemia symptoms on a 7-point Likert scale (lower scores indicate fewer symptoms) during the euglycemia and hypoglycemia portions of the clamp. In the unadjusted analyses, differences between euglycemic and hypoglycemic total scores on each diet will be compared using a paired t-test. Adjusted analyses will be based on LME, similar to the analyses described in Aims 1 and 2. In the secondary analysis, we will model mean hypoglycemia awareness score by domain (e.g., autonomic, neuroglycopenic, and malaise).

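### If participants are resampled, the percentile-bootstrap 95% interval for the adjusted Aim 1 difference covers only about 92% at n = 16; the plan does not name the resampling unit

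*Combined protocol and SAP*

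**What the plan says.** Section 6.5.1 plans a two-sided paired t-test for the unadjusted Aim 1 comparison. The adjusted analysis is a linear mixed model with a random intercept per subject, a diet effect, and age, BMI and diabetes duration as covariates. The adjusted difference is reported with "95% confidence intervals based on 500 bootstrapped samples (2.5th percentile and 97.5th percentile of the distribution". The resampling unit (participants, single rows or model-simulated data) is not given. Several CGM secondary outcomes are to be analysed in the same way.

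Two related places leave a unit or level open:

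- **Aim 2 (6.5.2).** A mixed model will "model the trajectories of change in mean levels of glucagon over time". A likelihood ratio test will "select between an LME model with just a random intercept or an LME with a random intercept and slope". Neither the grouping nor the slope variable is named. The section adds: "Effect sizes will be reported as the between-diet differences with bootstrapped 95% CIs". Section 6.4.2 relies on "models that specifically take into account within-person correlation in outcomes of interest".
- **Ketone days (6.5.1).** The proportion of days with elevated fasting ketones "during each diet period will be compared using paired-proportions z-test in the unadjusted analysis", then analysed by a mixed model with "a random intercept, link=logit for the binary outcome yes/no elevated levels with Bernoulli distribution". What is paired in the z-test is not stated.

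**The concern.** A percentile bootstrap of a mean from 16 paired differences has two known shortfalls. It uses what is in effect a normal quantile where a t quantile is needed, and its spread is based on a variance with divisor n, not n − 1. Both make the interval too short, and neither depends on the number of resamples. The interval attached to the primary outcome would then be labelled 95% without having that coverage. It could also disagree with the paired t-test of the same quantity, and the plan does not say which result governs.

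For Aim 2 and the ketone days, each clamp yields several samples and each diet period yields many days. A model-based test with only a participant-level intercept leaves out variation between a person's two clamps or two diet periods.

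**Working it through.** **Inputs.** From 6.4.2: 16 evaluable participants, 20 enrolled, effect 7.5 points, SD 10 used as the SD of the paired difference. From 6.5.1: two-sided alpha 0.05, 500 bootstrap samples, percentile limits. Assumed: complete pairs, baseline covariates, normal differences unless stated.

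**1. The plan's own figure.** A paired t-test with 15 df and noncentrality 0.75 × √16 = 3 has 80.06% power, and 16 / 0.80 = 20. The stated 80% and N = 20 reproduce.

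**2. What is being bootstrapped.** If covariates are constant within a person and pairs are complete, they cancel from the within-person contrast, so the model's diet coefficient is the mean paired difference. Fitted examples confirm this: in one data set both were 7.871, with a standard error of 2.796 for each.

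**3. Analytic coverage, participants resampled.** The interval behaves like mean ± 1.96 × √((n−1)/n) × SD/√n.

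- At n = 16 the effective multiplier is 1.96 × √(15/16) = 1.898. The t multiplier on 15 df is 2.131.
- Coverage is 2 × T₁₅(1.898) − 1 = 92.3%. Since 1 − 0.923 = 0.077, the interval can exclude zero when the t-test p lies between 0.05 and about 0.077.
- Width ratio: 1.898 / 2.131 = 0.89.
- Half-widths at SD 10: 1.898 × 10/4 = 4.7 points against 2.131 × 10/4 = 5.3 points.
- At n = 20 the same formula gives 92.9%.

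Coverage is free of scale, so it does not depend on the SD of 10.

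**4. Simulated coverage (B = 500, 20,000 trials for the normal-difference rows with participants resampled).**

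| Setting | Coverage |
|---|---|
| n = 16, participants resampled | 91.8% (width ratio 0.88) |
| n = 16, t interval | 95.1% |
| n = 20, participants resampled | 92.3-92.7% |
| n = 16, participants, B = 5000 | 92.0% |
| n = 16, participants, skewed (gamma) differences | 91.1% |
| n = 16, parametric bootstrap | 92.9% |
| n = 16, single rows, within-person correlation 0.3 / 0.5 / 0.7 (assumed), 1,500 trials | 96.7 / 96.9 / 97.5% |
| n = 16, bootstrap-t, participants resampled | 94.2% |

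A smaller run of row resampling (150 trials, 200 resamples) gave about 93 / 96 / 97%, with intervals 10-16% wider than the t interval. Row resampling is therefore generally too wide, but its exact coverage is less certain.

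**5. Disagreement with the t-test.** With participants resampled at n = 16, the bootstrap interval excludes zero while the t-test has p > 0.05 in about 3.3% of trials under the null, 9.4% at an effect of 0.5 and 6.0% at the planned 0.75.

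**6. Aim 2, illustration only.** The documents give no split of within-person variance. If the clamp accounts for 0 / 10 / 30 / 50% of it (assumed), a model-based test of the average diet difference with only a participant intercept has 5 / 10 / 22 / 32% false positives. A paired t-test on clamp means stays at 5%. If the planned bootstrapped interval resamples participants, clamp clustering is carried along, and zero is wrongly excluded in about 8% of trials at every share.

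**7. Ketone days, illustration only.** With 14 days per diet and a participant-by-period SD of 0 / 0.5 / 1.0 on the logit scale (assumed), the random-intercept model has 5 / 11-14 / 24-29% false positives. A participant-level z-test has about 7%, and a paired t-test on per-person proportions 5%.

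**The case against.** **The direction of the error depends on something the plan does not state.** This stands. A reader might infer that the interval is too short however it is computed. The documents do not support that, because row resampling would generally make it too wide. The shortfall is conditional on participant resampling.

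**BMI may not be constant within a person.** This also stands. Section 6.3.5 measures BMI at both clamp visits, and 6.5.1 does not say that the baseline value is used. With period-specific BMI the adjusted estimate need not equal the mean paired difference. A check with assumed BMI changes still gave coverage near 92-93%, so the size of the problem hardly moves, but step 2 rests on an assumption.

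**The practical effect is modest.** Fair. The gap is about 0.6 points in half-width, and 6.5.1 does not make exclusion of zero by this interval the decision rule. A reader might infer that the primary test has an inflated error rate; it does not, because the paired t-test is unaffected.

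**The t interval is not exact either.** True under skewness: with exponential differences it covered 91.4%, against 89.2% for the percentile interval.

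**Aim 2 and the ketone days.** A reader might infer that these comparisons carry false-positive rates of 20-30%. The documents do not support that. The rates need variance components the plan does not give and a particular reading of the random effects. For Aim 2, the plan reports diet differences with bootstrapped intervals, not with those model-based tests. For the ketone days, a yes/no Bernoulli outcome implies the day as the model's unit, and a subject-level intercept can be inferred from the Aim 1 sentence. What remains is a specification gap.

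**Conclusion.** The point holds in conditional form. If participants are resampled, pairs are complete and covariates are baseline values, the interval labelled 95% for the adjusted primary difference covers about 92% at n = 16 and 92-93% at n = 20, and it is about 12% narrower than the t interval. Full retention does not remove the shortfall. The unit has to be stated because the choice changes the interval in either direction. The CGM secondary outcomes inherit the same issue. The Aim 1 and Aim 2 paired t-tests and the sample size stand.

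The Aim 2 model and the ketone-day analysis need their unit and level stated. Model-based tests that omit clamp-level or period-level variation can exceed 5% false positives, by an amount the documents do not allow one to fix. These are minor clarifications beside the primary interval.

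**What to change.** **Main change.** In 6.5.1, make the main adjusted interval t-based with small-sample degrees of freedom (for example Kenward-Roger), and use the same for the CGM secondary outcomes. State whether BMI is the baseline value. If a bootstrap is kept in any aim, say that whole participants are resampled and use bootstrap-t as a sensitivity analysis.

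**Minor clarifications.**

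- Aim 2: name the grouping level and the slope variable. Either add a participant-by-diet (clamp) random intercept with small-sample df, or base the average diet comparison on per-participant clamp means. For response shape, the per-clamp summaries already promised in 6.4.2 ("We will also report the incremental rise and area under the curve (AUC) as well as mean and peak glucagon levels") can be compared by paired t-test.
- Ketone days: make the participant the unit of the unadjusted comparison, using per-participant proportions with a paired t or signed-rank test. Add a participant-by-period random intercept to the mixed model, with small-sample df.

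**Cost.** A few lines of SAP text and code. The primary interval becomes about 12-14% wider (1/0.89 = 1.12; 1/0.88 = 1.14), and its 95% coverage still assumes roughly normal differences. The added clamp intercept can be somewhat conservative when clamp variance is near zero (2.8% false positives at 15 df in simulation). Sample size, data collection and the planned paired t-tests do not change.

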#### Minimizing Risks:

- **Risks of Very Low Carbohydrate Diet:** In order to minimize the symptoms associated with transitioning to a low carbohydrate diet abruptly, participants will be encouraged to stay hydrated to help them acclimate and avoid unwanted symptoms.
- **Hypoglycemia/Hyperglycemia:** Participants will be contacted frequently during the course of the study. Blood draws will be done frequently during the HRU/CSRJU/Masonicare admission to minimize hypoglycemia and hyperglycemia. Intravenous glucose will be available in case hypoglycemia occurs. All infusates containing insulin are prepared under a filtration cabinet (Laminated HLDA filter) by qualified personnel using sterile disposable materials.
- Participants will be encouraged to monitor closely for signs of glycemic deterioration and will be able to contact our diabetes staff at any time if concerns arise.
- At the end of each visit, the participant will receive guidance for glucose monitoring, food intake, and insulin dosing as needed.
- During the study, insulin doses will be adjusted regularly (2-3 times per week as needed) to prevent hypoglycemia. Participants will use a real-time CGM that will provide alerts at the time of hypoglycemia and allow for early detection of hypoglycemia as well. Participants will be trained on treatment of hypoglycemia and to contact the study team immediately in any case of severe hypoglycemia.
- If any participant has 2 episodes of severe hypoglycemia, they will be transitioned to a regular diet after the 2nd episode of severe hypoglycemia.
- **Stable isotopes:** Isotopes will be carefully monitored, administered and will be prepared in the investigational pharmacy to ensure proper technique. As noted in

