### 5.2 Outcome Variables

#### 5.2.1 Primary Outcome Variables

**Aim 1:** The primary efficacy outcome will be the time spent in the target range of 70-180 mg/dL during the second week on each diet. Secondary safety outcomes will include the time spent in the hypoglycemic (less than 54 mg/dL, less than 70 mg/dL) and hyperglycemic (greater than 180 mg/dL, greater than 250 mg/dL) ranges. We will also measure the average sensor glucose values, standard deviation, and coefficient of variation during the second week on each diet period. We will compare average and range of fasting beta-hydroxybutyrate levels during each diet period. Number of episodes of diabetic ketoacidosis and severe hypoglycemic events during each period (baseline, diet periods, and washout period) will also be reported.

**Aim 2:** The primary safety outcome will be the mean levels of glucagon produced in response to hypoglycemia after each diet will be measured using a 2-step hyperinsulinemic euglycemic-hypoglycemic clamp. These will be measured after 15, 30, 45, and 60 minutes of euglycemia and hypoglycemia. Secondary safety outcomes will include mean levels of other counterregulatory hormones (cortisol, epinephrine, norepinephrine), and beta-hydroxybutyrate that are produced in response to hypoglycemia during the clamp will be compared after each 2-week diet period. Fasting levels of glucagon, free fatty acids, beta-hydroxybutyrate and IGF-1 (measure of growth hormone secretion), prior to the clamp will be compared after each diet period. Secondary outcome measures will include hepatic glucose production and adipose tissue lipolysis, which will be measured using stable isotope infusions during the euglycemic and hypoglycemic portions of the clamp. We will compare differences in hepatic glucose production during each clamp between a standard and very low carbohydrate diet. Additionally, deuterated water will be utilized to differentially evaluate the contribution of gluconeogenesis and glycogenolysis to endogenous glucose production.

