**Visit 2 Randomization (virtual/telephone or in person):**

- Anthropomorphic measures (weight, % body fat, % muscle mass, % water, % bone) – home or on scale in office.
- Insulin pumps and CGMs will be downloaded to assess glycemic control. The diabetes treatment regimen will be adjusted as clinically indicated.
  - If participants are starting the very low carbohydrate diet, insulin doses will be reduced by 10-20%, as clinically indicated, to prevent hypoglycemia.
- First diet will be assigned.
  - If participants are starting the very low carbohydrate diet, meals can be picked up 2-3 times per week at the metabolic kitchen located at Yale New Haven Hospital by study participants or by research staff. Research staff will work with participants to deliver the meals if they are unable to pick them up.
  - If we are unable to acquire meals from the metabolic kitchen, we will use a mail order meal service that provides information about macronutrient content of all meals provided that meet the standards of the dietary measures.
- Participants will be instructed to check daily fasting blood ketone levels.
- Participants will receive dietary instruction and review the dietary requirements of the study. Participants will be instructed to keep a dietary record (MyFitnessPal application, written, and/or with photos) for the duration of the dietary period.
- Participants will be instructed to call the pediatric diabetes emergency line (available 24/7) in any case of severe low blood sugar, elevated ketone levels, or symptoms of ketosis. Participants will also receive education on the treatment of hypoglycemia, we will ensure that all participants have glucagon at home.
- Participants will be contacted 3 times per week (2 scheduled, 1 unscheduled) for a 24-hour dietary recall. During these telephone follow up calls, food diary will be reviewed, ketone levels reviewed, and CGM data will be uploaded and reviewed.
- Prior to the HRU/CSRU/Masonicare admission, we will recommend a standard diet be given and no food be eaten after 9pm (except for in cases of hypoglycemia). Participants will be advised to limit exercise in the 3 days prior to study to limit acute effects of recent exercise on insulin sensitivity.

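### Time <54 and <70 mg/dL has no stated window; read literally, 6.5.1 compares these safety outcomes in week 2 only and leaves out the diet-transition week

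*Combined protocol and SAP*

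**What the plan says.** Section 6.5.1 places the primary endpoint, percent time in range, in the second week of each diet and describes its analysis: paired t-test, mixed model, bootstrap interval. It continues: "Secondary outcomes, including time spent with hypoglycemia (<54 mg/dL, <70 mg/dL", with the hyperglycemia ranges and mean sensor glucose, "will be analyzed similarly to the primary outcome". No separate window is given for these outcomes.

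The same section plans a Poisson mixed model for the "comparison of the number of episodes of diabetic ketoacidosis and severe hypoglycemic events during each period". Section 5.2.1 lists the periods meant: "severe hypoglycemic events during each period (baseline, diet periods, and washout period) will also be reported".

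The sections differ on the efficacy window. Section 5.2.1 uses "time spent in the target range of 70-180 mg/dL during the second week on each diet", while the Synopsis and the table in 6.2.1 use two weeks on each diet. All three list time <54 and <70 mg/dL as secondary safety outcomes. Section 6.5.3 (Safety) is marked not applicable.

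On insulin, the Visit 2 and Visit 4 text in 6.3.5 says that for participants starting the very low carbohydrate diet, "insulin doses will be reduced by 10-20%, as clinically indicated, to prevent hypoglycemia". Under Minimizing Risks, the protocol adds that during the study "insulin doses will be adjusted regularly (2-3 times per week as needed) to prevent hypoglycemia".

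**The concern.** A settling-in week can be reasonable for an efficacy endpoint meant to describe glycemia once the diet is established. It is harder to justify for a safety endpoint, because anyone who adopts the diet goes through the first week. The protocol treats that week as different: it specifies an insulin reduction at the start of one diet and not the other, and its risk section allows that a change of diet or insulin dose may worsen glycemia.

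If the hypoglycemia outcomes inherit the second-week window, the between-diet comparison describes only the settled state. Any week-1 difference in time <54 or <70 mg/dL, in either direction, would not appear in it. Because the window is unsettled across sections, it could also be chosen after the data are seen.

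**Working it through.** **1. The plan's own figure.** Section 6.4.2, Aim 1: effect size 7.5/10 = 0.75, paired t-test, two-sided alpha 0.05, 16 evaluable participants. With 15 degrees of freedom and noncentrality 0.75 × √16 = 3.0, power is 0.8006, and 16 is the smallest n that reaches 80%. 16/(1 − 0.20) = 20. The figures reproduce and do not depend on the CGM window. No effect size or SD is given for time in hypoglycemia.

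**2. Windows side by side.**

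| Section | Time in range | Mean glucose, SD, CV | Time <54, <70 | Severe events |
|---|---|---|---|---|
| Synopsis | 2 weeks | each 2-week period | not stated | each period |
| 5.2.1 | second week | second week | not stated | each period |
| 6.2.1 | 2 weeks | each 2-week period | not stated | each period |
| 6.5.1 | second week | mean glucose as for primary | as for primary | each period |

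Where 6.5.1 means the whole period, it says so, both for days with elevated ketones and for severe events. It has no such phrase for CGM hypoglycemia. The natural reading is therefore week 2.

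**3. Exposure left out.** 14 − 7 = 7 days per diet; 7/14 = 50%.

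**4. Effect on the reported mean.** Let m be mean time <70 in week 2 on one diet and k·m that in week 1. The 14-day mean is m(1 + k)/2, so the week-2 mean divided by the 14-day mean is 2/(1 + k). The documents do not give k; the values below are assumed.

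| k | Week-2 mean as % of 14-day mean |
|---|---|
| 0.5 | 133% |
| 1 | 100% |
| 1.5 | 80% |
| 2 | 67% |
| 3 | 50% |

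If k is the same on both diets, the two means are scaled alike. The contrast is distorted relative to the means only if k differs by diet.

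**5. Effect on power (illustration).** Assumptions: n = 16, equal SD of the paired difference in each week, between-week correlation ρ of 0.3 to 0.7, and a week-1 standardized difference d1 = 0.75. The 14-day standardized difference is ((d1 + d2)/2)/√((1 + ρ)/2).

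| Week-2 difference d2 | Week-2 test | 14-day test | Week-1 test |
|---|---|---|---|
| 0 | 5% (alpha only) | 33-41% | 80% |
| 0.375 | 29% | 63-74% | 80% |
| 0.75 | 80% | 86-94% | 80% |

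The formula is symmetric in d1 and d2. If the difference lay wholly in week 2 (d1 = 0, d2 = 0.75), the week-2 test would have 80% and the 14-day test 33-41%.

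**6. Severe events as a substitute.** As a simple gauge, an exact two-sided sign test on discordant participants gives 2 × 0.5^5 = 0.0625 with five all in one direction and 2 × 0.5^6 = 0.031 with six, so at least six are needed. With zero events, the one-sided 95% upper bound on the event proportion is 1 − 0.05^(1/16) = 17% for 16 participants and 1 − 0.05^(1/20) = 14% for 20. Severe events also do not measure time <54 or <70 mg/dL.

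**The case against.** The second-week window for hypoglycemia is inferred. The wording that ties the secondary outcomes to the primary follows a list of methods and may mean method only. If the two-week window of the Synopsis and 6.2.1 is adopted throughout, all 14 days are covered. This stands as a limit on certainty. It does not remove the problem, because settling the primary on week 2 would carry the safety outcomes with it unless a sentence separates them.

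Three stronger readings are tempting, and the documents do not support them.

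- A reader might infer that week 1 enters no hypoglycemia test at all. The Poisson model for severe events covers whole diet periods, so week 1 is in that test, weak as it is.
- A reader might infer that hypoglycemia is most likely in week 1. No section says so, and the insulin reduction is intended to prevent it.
- A reader might infer that leaving out week 1 flatters the very low carbohydrate diet. That needs k above 1 on that diet and a lower k on the standard diet. With k = 0.5, a week-2 window makes the test diet look worse. The titration two to three times a week applies on either diet, and the standard diet is itself prescribed, so its two weeks need not be alike.

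The week-1 data are also not lost to safety oversight: 6.2.2 has CGM data reviewed twice a week or more often. What is missing is their place in the between-diet comparison.

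**Conclusion.** The point holds in limited form. The documents disagree on the CGM window and give time <54 and <70 mg/dL none of its own. On the literal reading of 6.5.1, half of the on-diet days, including the transition, enter no CGM hypoglycemia comparison. Only severe-event counts then compare week 1, and with 16-20 participants they can show little.

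The size and direction of any distortion are unknown. Over assumed k from 0.5 to 3, the week-2 mean runs from 133% down to 50% of the 14-day mean on a diet. The case does not depend on week 1 being worse. It rests on these being labelled safety outcomes, on a transition step specified for one diet only, and on the lack of any stated reason to leave the transition out. The sample size and the primary test are unaffected.

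**What to change.** Reconcile the CGM windows across the Synopsis, 5.2.1, 6.2.1 and 6.5.1. In 5.2.1 and 6.5.1, state that percent time <54 and <70 mg/dL is compared between diets over all 14 days of each diet, whatever window is kept for time in range. For consistency, apply the same rule to the hyperglycemia ranges >180 and >250 mg/dL. Add a descriptive table of week 1 and week 2 by diet, so that a difference confined to either week can be seen even where the 14-day average dilutes it.

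The cost is a few sentences and one table. The CGM data are already collected; no visit, treatment rule, sample size or primary test changes. The one drawback is that safety and efficacy windows may differ and must be labelled wherever results are shown together.
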